All analyses will be intention-to-treat analyses—that is, data from parents and children will be analyzed based upon the condition to which they will be initially assigned, regardless of the number of classes they attended. This approach, although it reduces power, maintains the internal validity of the RCT design.⁵⁷ Because participants will be nested within classes, the intraclass correlations (ICC's) will be first examined for each dependent variable to determine if a statistical approach controlling for such nesting will be necessary. All outcome variables (except for child weight status) will be examined using multilevel analyses with the SPSS (version 25) Mixed Models Program. The SPSS Mixed Model program does not provide measures of effect sizes; however, 95% confidence intervals will be included for precision. Child sex, child age in months, and child BMIz at pre-test will be control variables in all of the multilevel analyses. Significant condition by time interactions will be followed up with simple main effects analyses and multi-level analyses comparing pairs of time points. The main analyses will be conducted on participants who have data at all 4 time points. Paired comparisons will use all available data. Most of the missing data will be addressed by calculating the subscale scores using the mean of the non-missing items in that particular subscale. If greater than 25% of a subscale's items are blank, then the score will be considered missing. The multilevel models also will be rerun examining (1 at a time) possible program moderators: child age, child sex, child BMI status, and location (Houston versus Pasco). Moderation will be tested by examining the significance of the moderator by condition by time interactions.

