Finally, to examine dosage effects, the multilevel analyses will be rerun for those variables showing significant condition by time interactions. In these analyses, only data from parents in the prevention conduction at post-test, 6-months, and 12-months will be examined to determine if the number of sessions parents attended predict their subsequent responses on questionnaire assessments (the pre-test assessments will not be included in these analyses because these sessions occurred *before* parents attend any classes). In conducting these analyses, the condition variable will be replaced by a variable assessing the number of lessons attended (values ranging from 0 to 7). To determine if the dosage effects vary by time point, a separate set of analyses will include the “lessons attended by time” interaction as a predictor (along with the corresponding main effects).

A multinomial logistic regression will be used to examine the effects of the program on children's BMI category (i.e., healthy weight, overweight, and obese). This regression will examine the main effect of condition, controlling for the same variables as in the multilevel

analyses (i.e., child sex, child age in months, and child BMI *z*-score at pretest).

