To control for Type I error, the critical *p* values for each assessment will be determined with the unweighted Bonferroni method,⁵⁸ dividing the critical value of *p* < .05 by the number of comparisons conducted for a given assessment. As discussed in Shaffer,⁵⁸ corrections for familywise error involve correcting alphas separately for each family of hypotheses. Although defining families is a rather straightforward process in a simple experiment (e.g., 1 family in a study with a single dependent variable and 1 independent variable with several levels), Shaffer argues that defining families becomes more complicated (and potentially more problematic) in large, more complex studies where alpha corrections can substantially lower statistical power (i.e., increase Type II error). To balance concerns about Type I and Type II error, a family will therefore be defined as the set of measures derived from a particular outcome assessment, and an alpha correction procedure will then be used (the unweighted Bonferroni) to control for error-rates within families. The resulting critical *p* values will be: FPI, 0.05/16 = 0.003; CFSQ, 0.05/3 = 0.017; FKQ, 0.05/6 = 0.008; compensation trials, 0.05/1 = 0.05; EAH, 0.05/1 = 0.05; FPQ, 0.05/2 = 0.025; CEBQ, 0.05/8 = 0.006; BMI, 0.05/2 = 0.025. Only results that meet these critical values will be reported in the primary analyses. To minimize the probability of Type II error, these critical values will be applied only to *p* values for the simple main effects analyses of time given the limited power of condition by time interactions in this type of design.⁵⁹

Finally, exploratory analyses will be run on variables that show condition by time interactions in the pre-post analyses reported by [name] and colleagues⁴⁵ but do not show significant interactions in the current study. Because the smaller samples at follow-up may reduce the power to find significant time by condition interactions at 6- and 12-months, simple main effects analyses of time were be run separately for the control and prevention groups to determine if the condition effects found in earlier pre-post analyses¹⁶ persisted for the variables in the current study.

REFERENCES

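### The stated within-family error control covers only within-arm tests of time; the randomised condition-by-time comparison has no corrected threshold

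*Combined protocol and SAP*

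**What the plan says.** In DATA ANALYSES, the paragraph on Type I error defines a family as the measures from one assessment and says that "an alpha correction procedure will then be used (the unweighted Bonferroni) to control for error-rates within families". It lists critical values of 0.05 divided by the number of measures: FPI 0.003 (16), CFSQ 0.017 (3), FKQ 0.008 (6), compensation trials 0.05 (1), EAH 0.05 (1), FPQ 0.025 (2), CEBQ 0.006 (8) and BMI 0.025 (2). It adds: "Only results that meet these critical values will be reported in the primary analyses". The next sentence limits their reach. It opens "To minimize the probability of Type II error, these critical values will be applied only to", and the tests that it then names are the simple effects of time; its reason is that interactions have little power in such a design.

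The exploratory paragraph that follows describes simple effects of time as run in each arm separately, so they are within-arm tests.

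The between-arm tests are set out earlier in the same section:

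- "All outcome variables (except for child weight status) will be examined using multilevel analyses". The interaction opens the follow-up: "Significant condition by time interactions will be followed up with simple main effects analyses and multi-level analyses comparing pairs of time points". No significance level is given for it.
- It also decides entry to the dosage analyses: "the multilevel analyses will be rerun for those variables showing significant condition by time interactions".
- BMI category is handled by multinomial regression: "This regression will examine the main effect of condition".

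**The concern.** In a two-arm trial with repeated assessments, evidence of a program effect is a difference between arms in change over time. Here that is the interaction. The plan announces control of error within families but attaches the thresholds to another hypothesis, namely whether one arm changed. A reader who sees 0.003 beside the FPI will take it to protect 16 between-arm comparisons, and it protects none of them directly.

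The BMI-category test is also left out. It is a main effect of condition, so it has no simple effect of time on which the listed 0.025 could act.

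The plan does not say which arm's time effect must pass for a finding to count. That choice alone changes the error rate a good deal.

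A separate, smaller matter is the exploratory step. It judges whether earlier condition effects persisted by testing time in each arm separately. Significant change in one arm and not in the other does not show that the arms differ.

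**Working it through.** **1. The plan's own figures.** 0.05/16 = 0.003125, 0.05/3 = 0.0167, 0.05/6 = 0.0083, 0.05/8 = 0.00625, 0.05/2 = 0.025 and 0.05/1 = 0.05. All eight listed values reproduce after rounding to three decimals. The arithmetic is right; the issue is which tests the values govern.

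**2. The interaction step alone.** At an assumed .05 with independent measures, the chance of at least one false interaction among k measures is 1 − 0.95^k: 56% for k = 16 (FPI), 34% for 8 (CEBQ as listed), 26% for 6 (FKQ), 14% for 3 (CFSQ) and 10% for 2 (FPQ). With between-measure correlation 0.5, the FPI figure is about 39%.

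**3. Both steps together.** A reported result must also show a time effect that meets the family threshold, so step 2 overstates the rate of false primary claims. I simulated the joint rule with no program effect. The documents give none of the following, so they are assumptions: 100 per arm, within-person correlation 0.6, between-measure correlation 0 to 0.5, the same step change in both arms from posttest onward, 3-df large-sample tests, interaction at .05 and time effect at .05/16. Two claim rules were used:

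- Either-arm: a time effect in either arm suffices.
- Strict: prevention passes and control does not.

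Chance of at least one false FPI claim (ranges span the two correlations and allow for simulation error):

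| Shared change | Subscales changing | Either-arm | Strict |
|---|---|---|---|
| none | – | 5–6% | 2–3% |
| 0.1 SD | all 16 | 16–22% | 8–12% |
| 0.2 SD | all 16 | 34–50% | 17–26% |
| 0.3 SD | all 16 | 39–56% | 12–19% |
| 0.5 SD | all 16 | 39–56% | under 1% |
| 0.2 SD | 4 of 16 | 16–20% | 8–10% |
| 0.5 SD | 4 of 16 | 18–22% | 2–3% |

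With .05/16 on the interaction itself, the rate is at most about 5%.

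**4. Other families** (same assumptions, 0.2 SD, all measures changing):

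| Family | Either-arm | Strict |
|---|---|---|
| CEBQ, 8 subscales | 24–31% | 11–14% |
| FKQ | 20–24% | 9–10% |
| CFSQ, or CEBQ with 3 subscales | 12–14% | 5% |
| FPQ | 9–10% | 3% |

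Compensation trials and EAH have a divisor of 1, so correction changes nothing.

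**5. Persistence step.** If both arms truly change alike and each within-arm test has power p, the pattern of prevention significant and control not occurs with probability p(1 − p). The maximum is 0.5 × 0.5 = 25%. At 100 per arm and 0.2 SD it is about 24% when tested at .05 and 18% at .05/16.

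**6. Power cost of correcting the interaction.** A contrast with 80% power at two-sided .05 has expected z = 1.960 + 0.842 = 2.802. The critical z at .05/16 is 2.955. Power becomes Φ(2.802 − 2.955) = Φ(−0.153) ≈ 44%. Restoring 80% needs ((2.955 + 0.842)/2.802)² ≈ 1.84 times the sample. The same formula gives 53% at .05/8, about 57% at .05/6, 66% at .05/3 and 71% at .05/2.

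**The case against.** The strongest defence is that this is an open trade-off. The plan says that it is balancing the two error types, says which tests the thresholds cover, and gives limited interaction power as its reason. The 44% figure shows that the loss is real. This stands, and it means that correcting the interaction cannot be called the only acceptable course. It does not rescue the statement that error is controlled within families, because the between-arm tests lack that control.

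A second defence is that a result must pass both steps. This stands in part. A reader might infer from step 2 that false FPI claims occur 56% of the time. The documents do not support that as the general rate, because the time test filters some false interactions. A reader might equally infer that the filter works only when neither arm changes. That is true of the either-arm rule, but under the strict rule the rate can also fall below 5% when shared change is large.

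A third is that the simulated rates depend on inputs and a claim rule that the documents do not give, and that the simulation omits the pairwise time comparisons, class nesting and covariates. This stands too. The rates are illustrations and do not estimate this trial's error.

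Finally, a false entry to the dosage analyses (up to 56% for FPI) might be read as a false efficacy finding. It is not: it only permits a further test of attendance within the prevention arm. The persistence step is labelled exploratory, which limits its weight but does not make a within-arm test a comparison of arms.

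**Conclusion.** The point holds on the text alone: the stated family-wise control does not extend to the condition-by-time interaction or to the condition effect on BMI category. A reader might infer that the plan conceals this, but the exemption is stated and reasoned. What is wrong is the claim of control that sits beside it.

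The practical effect is chiefly on FPI and FKQ, and on CEBQ if 8 subscales are tested. In CFSQ and FPQ the excess is small, or absent under the strict rule. Compensation trials and EAH are unaffected. BMI cannot be settled because its two measures are not named.

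The size depends on shared change over time. Such change is plausible in 3- to 5-year-olds assessed four times through a 12-month follow-up, but it is an assumption. The persistence inference is invalid as planned and ranks lower. Overall, this should be fixed; it does not by itself undermine the trial.

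**What to change.** 1. Choose one of two courses and state it.
   - Apply each family threshold to the overall condition-by-time test of each measure, and the BMI threshold to the condition effect on BMI category. The cost is the power loss in step 6 of the working.
   - Keep the exemption, withdraw the claim of family-wise control for between-arm findings in multi-measure families, label those findings as not multiplicity-controlled, and state which arm's time effect a claim requires. This is a change of wording and costs nothing.
2. Under either course, state the level used for the interaction and treat within-arm changes as descriptive. Reconcile the CEBQ divisor of 8 with the three subscales targeted in MEASURES, and name the two BMI measures.
3. Replace the separate within-arm persistence tests with between-arm differences in change at 6 and 12 months from the same model, with 95% confidence intervals, still labelled exploratory. This costs almost nothing.

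No new data are needed: the work is analysis-plan wording and, where the tests change, reanalysis.

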The goal of this study is to develop and test the efficacy of a scientifically-based, culturally competent seven-session parent directed, obesity prevention program focused on parental feeding strategies that support young children's self-regulation of intake.

STUDY DESIGN

A randomized controlled trial will be implemented across 2 sites (Houston, an urban city in Texas; and Pasco, an agricultural community in Washington) to examine the efficacy of the SEEDS childhood obesity prevention program. The prevention arm will receive parent and child program curriculums separately over 7 weeks for a total of 7 lessons. One lesson will be held each week with parent and child lessons held simultaneously. Each lesson will last about an hour. A combined family lesson (parent and child together) will be held before the parent and child lessons. All lessons will be held after the school day in Spanish at Head Start centers in Houston, TX and similar early education centers in Pasco, WA. The control arm will receive no curriculum. Approximately 8 to 10 families will participate in each of the prevention and control conditions at each wave. Parents will be asked if they could read and write in English or Spanish during eligibility screening so that assistance can be made available at the data collection sessions for those who need help completing the questionnaires. Participants in the prevention and control arms will complete the same assessments prior to the prevention program (pretest), after the program (posttest), and at 6- and 12-month follow-ups. Participants will be compensated \$40 at pretest, \$50 at posttest, \$60 at 6 months, and \$85 at 12 months.

FACILITATORS

Bilingual staff members will lead the face-to-face groups (i.e., parent, child, and family lessons). Parent facilitators will be required to have a graduate degree in psychology or education to optimize behavior change that is integrated into the program content. Child facilitators will be required to have training or experience in early childhood education. Family lessons will be co-facilitated by the parent and child facilitators. Facilitator training will include a 2-day intensive training session guided by study investigators which will include coverage of the program

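### The exploratory persistence step selects variables on an earlier pre-post result and judges them from the same pretest, so chance findings look more lasting than they are.

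*Combined protocol and SAP*

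**What the plan says.** The final paragraph of DATA ANALYSES sets two entry conditions. First, "exploratory analyses will be run on variables that show condition by time interactions in the pre-post analyses reported by" the study team in a cited report of the program's short-term effects. Second, the same variables qualify only if they "but do not show significant interactions in the current study". For these, "simple main effects analyses of time were be run separately for the control and prevention groups", in order "to determine if the condition effects found in earlier pre-post analyses" lasted. The reason given is loss of power: "Because the smaller samples at follow-up may reduce the power to find significant time by condition interactions at 6- and 12-months".

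STUDY DESIGN gives one pretest for all later comparisons: both arms "will complete the same assessments prior to the prevention program (pretest), after the program (posttest), and at 6- and 12-month follow-ups". On the analysis set, DATA ANALYSES says "The main analyses will be conducted on participants who have data at all 4 time points", while paired comparisons use all available data.

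The plan calls the step exploratory. It makes no allowance for the selection or the shared pretest. It does not say that the earlier report covers the same families, but the reference to smaller samples at follow-up, and the question of whether effects lasted, make sense only if it does.

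**The concern.** A pre-post interaction can be significant because the arms happened to differ at pretest. That same pretest is the starting point for the 6- and 12-month changes, so the chance difference carries forward. Choosing variables because the earlier test was significant picks out those where such differences were large.

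The rule also works one way. An outcome positive at posttest gets a second look after the four-visit test fails. An outcome null at posttest gets none, even if an effect emerges later. Because the plan reports in the primary analyses only results that meet the critical values, a reader may have no full set of outcomes to set beside the selected ones. At stake is the claim that program effects lasted to 6 or 12 months.

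**Working it through.** **Nothing to reproduce.** The plan gives no sample size, retention or error rate for this step.

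**Inputs from the documents.** Two entry conditions; one shared pretest; a within-arm test of time. The general rule divides the critical p value "< .05 by the number of comparisons conducted for a given assessment", giving 0.003 to 0.05 by assessment. These values are applied to simple main effects of time, but the plan does not say whether that covers the exploratory step.

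**Assumed.** 100 families per arm at pretest and posttest; 70% followed up at random; two-sided 0.05 for both the screen and the re-test; equal correlation between visits; no clustering by class; no program effect; no drift over time.

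**1. Correlation from the shared pretest.** With unit variances and common correlation ρ, two changes from the same pretest have covariance ρ − ρ − ρ + 1 = 1 − ρ, and each has variance 2(1 − ρ). Their correlation is 0.5 whatever ρ is. With 70% retained, the between-arm contrasts correlate 0.5 × √0.7 = 0.418. For the prevention arm alone the value is 0.418/√2 = 0.296.

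**2. Shift.** The mean of |Z| given |Z| > 1.96 is 0.0584/0.025 = 2.34. The first entry condition alone therefore shifts the later change by 2.34 × 0.418 = 0.98 standard errors (between-arm) or 2.34 × 0.296 = 0.69 (prevention arm). The second condition removes some of the larger departures. Simulation with both conditions gives about 0.87 and 0.61.

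**3. Frequency at 6 or 12 months, both conditions, 70% retention.** About 3.7% of null variables enter. Two comparators are possible for an unselected variable: significance in one fixed direction, or significance in the direction of its own pre-post change. The first removes both the selection and the shared pretest; the second removes only the selection.

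| Test | Selected | Own-direction comparator | Fixed-direction comparator |
|---|---|---|---|
| Prevention arm (planned) | 11.3% | 6.9% (ratio 1.6) | 4.5% (ratio 2.5) |
| Between-arm contrast | 14% | 7.7% (ratio 1.8) | 4.5% (ratio 3.1) |

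The planned test gave 11% to 12% across runs; at 11.7% the upper ratio is 11.7/4.5 = 2.6.

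**4. Sensitivity, prevention arm, pretest to 6 months only, both conditions.**

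| Retained | Two-sided, against 0.05 | Earlier direction, against 0.025 |
|---|---|---|
| 100% | 0.081 (1.6) | 0.080 (3.2) |
| 75% | 0.069 (1.4) | 0.068 (2.7) |
| 60% | 0.061 (1.2) | 0.058 (2.3) |

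Counting either visit in the earlier direction, over retention of 0.6 to 1.0 and equal or autoregressive correlation, gives 10.5% to 15.8% against 4.0% to 4.6%, or 2.3 to 3.9 times. If the 0.003 critical value applied, at 75% retention the single-visit two-sided rate would be 0.0034 against 0.0029, or 1.2 times.

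**5. Overall frequency.** 3.7% × 11.3% = 0.4% of null variables both enter the step and appear to persist.

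**6. Drift.** If both arms drift with an expected z of 2 from pretest to 6 months, the prevention-arm test is significant in about 51% of null cases, selected or not. That error comes from testing within arms and is separate from the selection.

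**The case against.** The case against has real force. The step is labelled exploratory, its entry rule is stated openly, and asking whether an effect lasted naturally concerns variables that showed one. Sample size, retention and both alphas are assumed. Only about 0.4% of null variables would yield a false persistence claim. Testing every outcome instead would give each null variable about a 4.5% chance of a false result in one direction, or about 9% in either. With drift, the within-arm test is the larger weakness.

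All of that stands as a limit on size. It also bars three stronger readings. A reader might infer that chance findings appear to persist three times as often as they should. That figure comes from a between-arm contrast the plan does not run, set against a fixed-direction comparator, or from particular ways of counting direction. A reader might also infer a high overall error rate; rare entry rules that out. Finally, a reader might infer that outcomes null at posttest are never tested at follow-up. In fact, every outcome except child weight status goes into the four-visit model. What those outcomes lack is the second look.

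The objection does not remove the fault. The exploratory label does not tell a reader that the selected estimates are shifted, and the four-visit model does not supply a visible unselected set when primary reporting is limited to results that meet the critical values. The worry about multiplying tests is a reason to report estimates without significance claims, not a reason to keep the entry rule.

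**Conclusion.** The point holds in direction and is moderate in size. Selection on the earlier result, combined with the shared pretest, moves later changes toward the earlier direction by roughly 0.6 standard errors for the planned prevention-arm test and 0.9 for a between-arm contrast. For the planned test at 70% retention, apparent persistence is about 1.6 to 2.6 times as frequent as for an unselected variable. Across the retention levels, directions and tests worked through here, the range is roughly 1.2 to 4 times, and no single multiple should be quoted as the answer. These sizes assume no true effect and no drift. The point also depends on the earlier report covering the same families, which the text implies but does not state. The practical harm is over-reading the few variables that enter and giving no second look to those that were null at posttest.

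**What to change.** In the final paragraph of DATA ANALYSES, replace the significance-based entry rule. For every outcome, give the between-arm difference in change from pretest to 6 months and from pretest to 12 months, with 95% confidence intervals, in one exploratory table. Present these as estimates, without significance claims, and mark the outcomes that were significant in the earlier report. State that the marked estimates are selected and likely to be too large, and make no persistence claim from the marked subset alone. Say explicitly whether the earlier report covers the same families.

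The cost is wording, a longer exploratory table and some additional model fits, because the plan otherwise compares pairs of time points only after a significant interaction. No new data are needed. The use of within-arm tests to judge a condition effect is a separate fault, and the case for this change does not rest on it.

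### The exploratory step at the end of DATA ANALYSES judges whether between-arm effects persisted from separate within-arm tests of time, with no between-arm contrast

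*Combined protocol and SAP*

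**What the plan says.** All of this is in the DATA ANALYSES section of the combined protocol and SAP.

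- **Entry to the step.** Its last paragraph says that "exploratory analyses will be run on variables that show condition by time interactions in the pre-post analyses" of an earlier publication, provided that they "do not show significant interactions in the current study".
- **Reason given.** "Because the smaller samples at follow-up may reduce the power to find significant time by condition interactions at 6- and 12-months".
- **Test.** "simple main effects analyses of time were be run separately for the control and prevention groups to determine if the condition effects found" in the earlier analyses have persisted.
- **Follow-up in the main analysis.** The first paragraph of the section says: "Significant condition by time interactions will be followed up with simple main effects analyses and multi-level analyses comparing pairs of time points". Variables in the exploratory step have no significant interaction, so this provision does not reach them.
- **Data used.** "The main analyses will be conducted on participants who have data at all 4 time points", whereas "Paired comparisons will use all available data".
- **Critical values.** The Bonferroni values, from 0.05/16 to 0.05/1, are applied only to p "values for the simple main effects analyses of time given the limited power of condition by time interactions". The exploratory step uses the same term for its tests, so the values may carry over to it; the plan does not say.

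The first paragraph also promises 95% confidence intervals in general terms. The exploratory step does not make a between-arm interval the basis for deciding persistence, and it does not say how the two arms' results are to be read together.

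**The concern.** The question asked is about a between-arm effect, but the tests answer two separate within-arm questions. A significant change in one arm and a non-significant change in the other is not evidence that the changes differ.

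The gap matters when both arms change together. The documents make that plausible. The background reports that older children compensate less well than younger ones. The Food Preferences Questionnaire counts fruits and vegetables tried, which would be expected to rise with age in either arm. Both arms also complete the same assessments four times. With a shared change, one arm can cross the critical value and the other miss it by chance, and the result could be reported as a program effect lasting to 6 or 12 months. For these variables the one between-arm test in the plan has already come out non-significant.

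**Working it through.** **Plan's own figures.** The critical values reproduce: 0.05/16 = 0.003125 (printed 0.003), 0.05/3 = 0.0167 (0.017), 0.05/6 = 0.0083 (0.008), 0.05/8 = 0.00625 (0.006), 0.05/2 = 0.025, 0.05/1 = 0.05. The plan states no total sample size, SD, dropout or power.

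**Assumptions.** Normal approximation; independent arms with equal standard errors (SE); clustering not modelled; one two-sided test of change per arm. The reading is that prevention is significant in the favourable direction and control is not. Let z1 (prevention) and z2 (control) each be N(θ, 1), where θ is the common true change divided by the SE of a within-arm change. There is then no condition effect. With c the critical value:

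P(pattern) = P(z1 > c) × P(|z2| < c)

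At c = 1.960 (level 0.05):
- θ = 0: 0.025 × 0.950 = 0.024
- θ = 1: 0.169 × 0.830 = 0.140
- θ = 1.96: 0.500 × 0.500 = 0.250
- θ = 3: 0.851 × 0.149 = 0.127

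The step admits only variables with a non-significant interaction. I represent that by requiring |z1 − z2|/√2 < 1.96 and integrate numerically:

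| Level | Condition | θ = 0 | θ = 1 | θ = 1.96 | θ = 3 |
|---|---|---|---|---|---|
| 0.05 | none | 2.4% | 14% | 25% | 13% |
| 0.05 | contrast non-significant | 1.7% | 13% | 24% | 11% |
| 0.05/16 (c = 2.955) | none | 0.2% | 2.5% | 13% | 25% |
| 0.05/16 | contrast non-significant | 0.1% | 1.7% | 12% | 24% |

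At θ = c the formula is close to 0.5 × 0.5, so the peak is 25% at every listed critical value. Bonferroni moves it from a common change of 1.96 SE to one of 2.96 SE. A single direct between-arm test at 0.05 errs 2.5% of the time in the favourable direction, whatever the common change.

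**Does the step remedy low power?** Take a true difference that a direct test detects 80% of the time: 2.80 SE of the contrast, or 2.80 × √2 = 3.96 SE of a within-arm change. Let z2 be N(b, 1) and z1 be N(b + 3.96, 1), where b is the control-arm change. About 20% of such variables have a non-significant contrast and so enter the step. Among those, the pattern appears:

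| Level | b = 0 | b = 1 | b = 1.96 | b = 3 |
|---|---|---|---|---|
| 0.05 | 80% | 49% | 10% | 0.4% |
| 0.05/16 | 51% | 80% | 50% | 9% |

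The same true difference is found often or almost never, depending on a control-arm change that nobody knows in advance.

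**The case against.** The strongest reply is that the step is labelled exploratory, adds to the main interaction test without replacing it, and concerns variables whose non-significant between-arm result is already part of the main analysis. That stands, and it limits the reach to statements about persistence at 6 and 12 months.

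A second reply is that the plan never says that prevention significant, control not means persistence. That also stands. Every percentage above rests on that assumed reading. With no common change the rate, 2.4%, is about that of a direct test. The 25% is a maximum, not an estimate for this trial.

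Third, the rates condition on the non-significant contrast in the current study but not on the earlier significant pre-post result, which is also an entry rule. The effect of that omission was not worked out. If the step means one overall test of time per arm across all visits, the single-test figures do not apply directly, though the logical gap is the same.

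A reader might infer more: that the trial's main conclusions rest on within-arm tests, or that its false-positive rate is 25%. The documents support neither. The main analysis tests the condition by time interaction, and the documents give nothing from which the common change could be fixed. None of these replies turns two within-arm tests into a test of a between-arm difference.

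**Conclusion.** The point holds for the exploratory step only. As written, the step can yield a statement that a condition effect persisted without any between-arm evidence for it. Under the assumed reading and an equal true change in both arms, the misleading pattern occurs in about 2% to 25% of cases per test at 0.05 (1.7% to 24% given a non-significant contrast), depending on an unknown common change. Stricter critical values do not lower the peak. Low interaction power is a fair worry, but separate within-arm tests do not reliably answer it. This should be corrected, at lower priority than a defect in the main analysis.

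**What to change.** Replace the last sentence of DATA ANALYSES with:

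> For these variables the between-arm difference in change from pretest to 6 months and from pretest to 12 months will be estimated with 95% confidence intervals from multilevel models of those pairs of time points, using all available data. An effect will be described as persisting at a follow-up only if the between-arm interval excludes zero in the same direction as the earlier pre-post effect. Otherwise persistence will be described as not shown, and the estimate and interval will be reported, including any interval that lies wholly in the opposite direction. Within-arm changes are descriptive. The analysis is exploratory, the intervals are not adjusted for multiplicity, and the number of variables and intervals examined will be reported.

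This meets the power concern as far as the data allow, because the paired models are not restricted to participants seen at all four time points.

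The cost is two extra models per variable, of a kind the plan already uses after significant interactions, and no new data. Some results that might have been called persistent no longer will be. Two unadjusted intervals per variable carry about 4% to 5% error in the favourable direction (4.8% to 4.2% for correlations of 0.3 to 0.7 between the two contrasts, before conditioning on entry), not 2.5%; hence the requirement to report how many were examined.
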